1 PROTOCOL SUMMARY

1.1 SYNOPSIS

Title:	Utilizing CT Based Imaging Parameters of Body Composition to Understand Heterogeneity of Response to Biologic Therapies in Severe Asthma Cohorts							
Study Description:	We plan to utilize University of Michigan EMR data to form a retrospective cohort of severe asthma patients on biologic therapies for asthma with CT imaging and known outcomes on therapy. We will then analyze these images using morphomics, a combination of high-throughput image analysis and deep learning techniques, to derive imaging biomarkers that will be able to predict therapeutic response to biologics. These biomarkers will then be tested in a second cohort from the University of Calgary to assess for validity.							

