Recent studies have shown that these digital biomarkers extracted by analytic morphomics provide much better quantitative understanding of morphological features of the human body^{7,8}. More importantly, morphomics has been shown to significantly and substantially improve the prediction of clinical outcome and cost in numerous patient populations^{9,10}. By providing a quantitative measure of a patient’s body compartment dimensions and composition, near the time of treatment, morphomics can deliver tailoring variables for clinical decision-making.

More recently, morphomic measurements of rib length, density, shape, and angle have allowed a level of analysis of the chest wall that has never been studied in asthma patients^{11,12,13}. Using adjacent ribs as a reference, we have then been able to measure intercostal muscle size and quality (**Figure 3**). Morphomics has previously demonstrated the role the chest wall can play in disease by linking rib angle and age to potentially explain the higher incidence of rib fractures in the elderly in motor vehicle collisions¹⁴. Since severe asthmatics typically have air trapping and are at risk for obesity, it follows that they would also have abnormal chest wall anatomy that could be mechanistically contributing to their disease in a way that could significantly impair their response to medical therapies. The specific characterization of chest wall anatomy in severe asthmatics has never been studied and represents an opportunity to identify novel biomarkers that could predict response/non-response to therapies and enrich the selection of patients in future targeted asthma studies of all levels of severity.

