4 STUDY DESIGN

4.1 OVERALL DESIGN

Over an 18-month period we plan to conduct our study in 3 parts as identified in the study timeline table above.

University of Michigan Cohort Discovery, Database Construction, and Baseline Analysis

We plan to utilize existing data analytic tools at the University of Michigan to search the EMR for eligible patients to include in a retrospective cohort as identified by the inclusion criteria in section 5. We estimate that approximately 300 subjects will meet our initial criteria based on a preliminary search. We will then abstract all available clinical information from the EMR, de-identify it (with coded key stored in a separate, secured location), and enter the resulting coded data into a database. Up to 2 years prior to biologic initiation or CT scan (whichever is earlier) and all post-biologic therapy information will be included. Clinical information we will abstract will include demographic information, heights, weights, comorbid illnesses (coded as malignancy, coronary artery disease, diabetes, stroke/TIA, cirrhosis, and CKD), non-biologic asthma medication dosage and frequency of use (OCS, ICS, SABA, LAMA, LABA, montelukast, zileuton, and theophylline), asthma biologic agent (benralizumab, reslizumab, mepolizumab, omalizumab, and dupilumab) start and (if applicable) end dates as well as reason for end date (coded as ineffective, cost, intolerance/allergy, non-compliance, lost to follow-up, and other), FeNO, ACT scores, serum and sputum eosinophil counts, IgE, pulmonary function test parameters (% predicted), hospital/emergency room/urgent care/unscheduled office visits and phone call encounters for asthma or breathing-related complaints, and subjective clinician assessment of asthma control (independently graded by 2 different clinicians interpretation of EMR data). Each subject will also be assigned a phenotype by the Severe Asthma Research Program criteria¹⁵. If a majority of subjects are missing post-bronchodilator data and unable to be clustered by these criteria, we will instead assign adopted clusters from this paper as follows: Cluster 3-Normal FEV1 ($\geq 68\%$ of predicted), eosinophils (< 200 cells/ μL), FeNO (< 25 ppb), and IgE (< 200 UI/ml) and no evidence of atopy; Cluster 4-Reduced FEV1 ($\leq 68\%$ of predicted) with abnormal elevation of eosinophils, FeNO, or IgE and/or evidence of atopy; Cluster 5--Reduced FEV1 ($\leq 68\%$ of predicted) with normal eosinophils, FeNO, or IgE and no evidence of atopy. We do not expect to have any Cluster 1 or 2 patients in our study but will assign them accordingly if present. We will perform similar abstraction procedures for approximately 200 patients in the University of Calgary cohort, and label the data with a tag for this cohort for analytical purposes.

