
For the purposes of our analysis, we will define baseline measurements as the average of all data obtained in the year prior to biologic initiation or, if only one clinical encounter (defined as an office or emergency room visit) is available in this time period, then the average of the 2 clinical encounters immediately prior to biologic initiation will be used with the time frame noted in the database. In order to assess our primary and secondary outcomes we will use the average of all data from 4 to 18 months after biologic initiation or, if only one clinical encounter is available in this time period, the average of the 2 clinical encounters closest to, but not before 4 months after, biologic initiation. If a second biologic is introduced or the initial biologic choice is

changed, we will use all clinical data prior to the change, even if it is before 4 months of use, then follow the above steps to collect new outcome data on the new drug (see **Figure 4**).

[figure not shown]

Figure 4. Baseline and Response Clinical Data Plan.

Since our interest is primarily in finding the ~15% of patients who do not respond to biologics, we have chosen to include partial and complete responders together in our endpoints in order to isolate the non-responder population. Table 1 below will represent the dichotomization of responders and non-responders for each endpoint using the baseline and post-biologic data as detailed above. An exacerbation will be defined as any hospitalization, urgent care, emergency room, or unscheduled office visit for asthma or a breathing-related complaint or a temporary increase of OCS or ICS dosing for 3 or more days with the intent of the increase to treat acute symptoms. For clinician response, clinical encounter notes will be read and interpreted by 2 independent physicians and graded as detailed in the table. Upon completion of all data abstraction the patient will be de-identified as described in data handling below.

	Responder	Non-responder
Exacerbations	Any decrease from baseline	No change from baseline
Hospitalizations	Any decrease from baseline	No change from baseline
Maintenance oral corticosteroid (OCS) use	Any decrease from baseline	No change from baseline

Change in FEV1	$\geq 5\%$ improvement from baseline	<5% improvement from baseline
ACT score	≥ 1 -point improvement from baseline	No change from baseline
Clinician impression of response to therapy	Any improvement in symptoms from baseline	No change from baseline

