Table 1. Outcome Response Grading.

Morphomics CT Analysis and Clustering

After identification of all appropriate patients in the University of Michigan cohort, we will then identify all relevant CT scans in subjects. We will select pre-biologic CT data of the chest and, if available, abdomen/pelvis (or if no pre-biologic scans exist for a subject we will utilize CT imaging closest to the biologic start date and make note that the CT scan was obtained after biologic initiation) for analysis. Height-normalized measures will be computed to control for height-related correlation (e.g., Skeletal Muscle Index = Skeletal Muscle Area / Height²). Morphomics analysis will be run with measures centered and scaled into standard deviation units, stratified by sex and age. In addition, the Reference Analytic Morphomics Population¹⁶ will be used to generate additional variables that offer a population-based control for sex and age.

Analysis of Phenotypes, Training Data Set, and Assessing Model Robustness

Please see the statistical section for detailed statistical analysis plan.

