5 STUDY POPULATION

5.1 INCLUSION CRITERIA

Our population will include all adults 18 years or older with a diagnosis of asthma (defined as a positive methacholine test, supportive PFTs, or clinician diagnosis with appropriate supporting clinical context) who have been prescribed and taken an FDA-approved biologic medication for severe asthma (mepolizumab, benralizumab, reslizumab, omalizumab, or dupilumab) and have chest CT images in the University of Michigan radiology databases. All patients from the Calgary cohort will be screened in a similar fashion.

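### A CT taken after the biologic started can serve as the predictor with no limit on delay, and no planned analysis uses the note that marks such scans

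*Combined protocol and SAP*

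**What the plan says.** All references are to the combined protocol and SAP.

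- **CT selection (4.1, Morphomics CT Analysis and Clustering).** The default is a chest CT from before the biologic. Otherwise, "if no pre-biologic scans exist for a subject we will utilize CT imaging closest to the biologic start date and make note" that it postdates initiation. The scan then goes into the analysis.
- **Eligibility (5.1, 5.2).** Patients must "have chest CT images in the University of Michigan radiology databases". Neither section dates the CT relative to treatment.
- **Outcome window (4.1).** For the primary and secondary outcomes "we will use the average of all data from 4 to 18 months after biologic initiation", with a fallback when encounters are few.
- **Change of biologic (4.1).** Data before the change are used for the first drug; the team will "then follow the above steps to collect new outcome data on the new drug".
- **Calgary (4.1, 5.1).** "We will perform similar abstraction procedures for approximately 200 patients in the University of Calgary cohort", and "All patients from the Calgary cohort will be screened in a similar fashion". The CT selection text itself speaks of the Michigan cohort.
- **Purpose.** The section 3 objectives are worded as associations. The Synopsis, however, intends "to derive imaging biomarkers that will be able to predict therapeutic response to biologics", and section 2.2 says that "near the time of treatment, morphomics can deliver tailoring variables for clinical decision-making". Section 3 justifies the primary endpoint by its value to clinicians deciding whether to start a biologic.
- **Analysis (6.1 to 6.3).** The plan covers height and sex scaling, optional age and sex percentiles, CART, clustering, elastic net, random forest, gradient boosting, sample splitting and evaluation in Calgary. None of these refers to CT timing. Section 7.2 adds nothing.

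**The concern.** A predictor should be measured before the outcome it predicts. A scan taken on treatment may carry the effect of the drug or of the response itself, for example through weight change or lower oral steroid exposure. In patients with such scans, a CT measure could be associated with response without being informative when the treatment decision is made. The opposite is also possible: a real pre-treatment association could be masked.

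The reason for scanning may matter too. Section 4.2 says that stable asthmatics rarely have a CT, although asthmatics are scanned for various reasons. Some post-start scans may therefore have been prompted by trouble on treatment, which lies close to the exacerbation outcome.

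At stake is the predictive claim. As written, the plan would leave a reader unable to tell whether a selected biomarker depends on post-start scans.

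**Working it through.** **1. Is the delay capped anywhere?** No. Choosing the closest scan ranks the available scans but sets no limit. The two-year limit in 4.1 governs abstraction of clinical data, not the CT date. A patient whose only chest CT was taken at month 18 or later can be eligible under 5.1 and 5.2. That CT is then the predictor of an outcome measured in months 4 to 18.

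**2. Would the planned checks reveal a problem?** Sample splitting would not, because both parts would contain post-start scans. Calgary would not necessarily do so either: if the same fallback is used there, the same artefact could recur.

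**3. How large could it be?** The plan has no figure to reproduce; its 300 is a count from a preliminary search, not a power calculation. The following are assumptions:
- a share s of scans is post-start, equal in responders and non-responders (20% or 40%);
- responders' post-start scans shift by d SD relative to non-responders' (0.1 to 0.5).

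For a measure with no pre-treatment value, AUC = (1 − s) × 0.5 + s × Φ(d/√2).

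| s | d = 0.1 | d = 0.3 | d = 0.5 |
|---|---|---|---|
| 20% | 0.506 | 0.517 | 0.528 |
| 40% | 0.511 | 0.534 | 0.555 |

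For a measure with true AUC 0.70 (separation 0.742 SD), AUC = (1 − s) × 0.70 + s × Φ((0.742 ± d)/√2). This gives 0.705 to 0.744 if the shift adds to the signal and 0.647 to 0.695 if it opposes it.

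**4. What precision does a pre-start subset lose?** Take 15% non-responders, the share given in 4.1. Applying it to any single endpoint is an assumption. Michigan: 0.15 × 300 = 45 non-responders and 255 responders, before the follow-up exclusion. Calgary: 0.15 × 200 = 30 and 170. Half-widths are 1.96 × the Hanley-McNeil SE at an assumed AUC of 0.70.

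| Set | Michigan | Half-width | Calgary | Half-width |
|---|---|---|---|---|
| All | 45/255 | 0.090 | 30/170 | 0.111 |
| 20% removed | 36/204 | 0.101 | 24/136 | 0.124 |
| 40% removed | 27/153 | 0.117 | 18/102 | 0.143 |

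**5. What can the repeat show?** For a null measure, SE = √((m + n + 1)/(12mn)), with m non-responders and n responders. At Michigan this is 0.0468 for 45/255, 0.0523 for 36/204 and 0.0604 for 27/153. The subset lies within the full set, so the variance of the AUC difference is roughly the subset variance minus the full-set variance.
- s = 20%, d = 0.3: expected gap 0.017; half-width 1.96 × √(0.0523² − 0.0468²) = 0.046.
- s = 40%, d = 0.5: expected gap 0.055; half-width 1.96 × √(0.0604² − 0.0468²) = 0.075.

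In both cases the expected gap is smaller than its sampling error.

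**6. Would restricting the main analysis be better?** Compare √(bias² + SE²) for a null measure. At 20% and 0.3 SD it is 0.050 with all patients and 0.052 restricted. At 40% and 0.5 SD it is 0.073 and 0.060. Neither choice wins throughout.

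**The case against.** The strongest reply is that the plan has already dealt sensibly with imperfect retrospective data. It prefers pre-biologic scans, takes the nearest one otherwise, and marks it. The objectives are associations. The assumed bias lies within the sampling error of the full set (at most 0.055 against a half-width of 0.090), and a subset repeat could not reliably detect it.

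Much of this stands. The note deserves credit, because it makes the check feasible. The low power of the comparison is a good reason not to use the repeat as a pass/fail test. But recording a flag is not analysing it, and the wording of the objectives does not remove the stated predictive use. A systematic bias also does not shrink as the sample grows, and a small expected bias under assumed inputs is no evidence that the actual one is small.

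Some stronger readings are tempting but not supported:
- A reader might infer that the results will be materially biased. The documents give neither the share nor the shift, so the effect may be negligible.
- A reader might infer that post-start scans pass through the section 6.2 clusters into the outcome models. Sections 1.1 and 6.3 do not say that those clusters are predictors.
- A reader might fear that scan dates are lost at anonymization. Section 4.1 uses the CT date to set the abstraction window, and section 7.1.9.1 keeps a key to the medical record number.
- A reader might want only scans from before a patient's first biologic to count. For a patient who switched, a scan between drugs still precedes the second treatment decision. Figure 4 is not shown and might bear on switching.

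**Conclusion.** The concern holds as a gap in design and analysis. The plan admits predictors measured after treatment start, with no limit on delay and no analysis that uses the flag, while intending to predict response. Its size cannot be computed from the documents. The null AUC of about 0.51 to 0.56 rests entirely on assumed shares, shifts and equal shares by response. The precision figures also assume 15% non-responders on the endpoint in question. This does not invalidate the study, and post-start scans need not be excluded from the main analysis. It is a cheap improvement that should be made before modelling starts.

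**What to change.** Add to section 6.3:

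1. Repeat the outcome models and the Calgary evaluation, refitted only in patients whose CT was taken on or before the start of the biologic being assessed. Present the result beside the full-set result.
2. Report the share of post-start scans and the CT-to-start interval by response group and site. State that one CT timing rule applies at both sites.
3. For patients who switched, state which start date defines a pre-biologic scan, and flag scans taken on an earlier biologic.
4. If section 6.2 clusters serve as predictors in the repeat, derive them without post-start scans.
5. State that findings resting on post-start scans are associations, and that the repeat is a descriptive consistency check, not a gate.

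The cost is a little more analysis on data already held and a less precise subset: at Michigan, under the assumptions above, the half-width rises from 0.090 to 0.101 or 0.117. No new patients or scans are needed.

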Secondary Objectives:	
1. To identify imaging biomarkers that are associated with the probability of any post-treatment improvement of FEV1 of 5% or more2. To identify imaging biomarkers that are associated with the probability of any post-treatment reduction in maintenance OCS use							
Exploratory Objectives:	
1. To identify imaging biomarkers that are associated with the probability of any reduction in pre-treatment baseline hospitalizations for asthma2. To identify imaging biomarkers that are associated with the probability of any post-treatment improvement in ACT score3. To identify imaging biomarkers that are associated with the probability of any subjective post-treatment reduction in symptoms described clinically							
Endpoints:	Primary Endpoint:	Determine the cutoff value in chest wall muscle size/quality that optimally classifies patients that had and did not have any reduction in pre-treatment baseline exacerbation frequency (binary). Alternative (continuous): determine the strength of the linear/non-linear relationship						

	between continuous chest wall muscle size/quality and continuous change in exacerbation frequency
Secondary Endpoints:	
 1. Determine individual and combinations of body composition measures (phenotypes) associated with a 5% or greater improvement in FEV1 when compared to baseline FEV1 2. Determine individual and combinations of body composition measures associated with any reduction in maintenance OCS use when compared to baseline OCS use
Exploratory Endpoints:	
These endpoints may be limited in scope of analysis by the sample size within each of the outcome groups.
 
 1. Determine individual and combinations of body composition measures associated with any reduction in hospitalizations when compared to baseline hospitalizations 2. Determine individual and combinations of body composition measures associated with any improvement in ACT score when compared to baseline ACT score 3. Determine individual and combinations of body composition measures associated with any subjective improvement of symptoms when compared to baseline symptoms

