2.2 BACKGROUND

Innovation—Expanding on the Role of Body Composition

Nearly all research in severe asthma patients, including phase 3 trials for the current biologic therapies, has used BMI as a surrogate of body composition. Even when CT imaging has been used to better characterize body composition through relatively simplistic maneuvers such as calculation of total visceral and subcutaneous fat mass there have been no clinically usable predictive results from such analyses and no information about the role of the chest wall^{3,4}. Morphomics is a combination of high-throughput image analysis and deep learning techniques that enable the segmentation of tissues to precise detail, enabling the characterization of body composition to an unparalleled degree^{5,6}. Furthermore, the University of Michigan analytic morphomics group has an existing relational database of over 120,000 subjects that enables the generation of thousands of precise measurements, such as fat distribution, bone mineral density, and muscle density and size, and that can serve as a reference population for our asthma cohorts. This will allow for the accurate identification of extensive body composition patterns that differ from the norm utilizing an imaging population database on a scale that has never been done before.

Analytic morphomics provides actionable quantification of patient heterogeneity for precision medicine.

Precision medical intervention requires granular, precise, and actionable data at the time of treatment. Supported by rapid advances in new high-throughput technologies, “omics” data provide a unique opportunity to better understand pathophysiology and to translate research findings to clinical practice. These data enable clinicians to shift from traditional one-size-fits-all

treatment toward more targeted and precisely individualized therapies. Over the past decade, research at the University of Michigan has demonstrated that **morphomics** is the “omics” data most proximate to a patient’s ultimate health outcome (**Figure 2**).

[figure not shown]
[figure not shown]

Figure 2: Morphomics is the "omics" most proximate to treatment

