4.2 SCIENTIFIC RATIONALE FOR STUDY DESIGN

We elected to approach this problem in a retrospective fashion due to the availability of existing data that is likely sufficient to answer our clinical question and the known risks of radiation from CT exposure. Many asthmatics undergo CT scans for various reasons; however, it is rare to obtain a CT scan in a stable asthmatic, even if symptoms are severe, since there is no known current clinical utility in this diagnostic test. Since our question relies on using CT data to assess body composition in severe asthmatics requiring biologics to find novel parameters that may be able to predict response more reliably than the current standard of care options (FeNO, sputum/serum eosinophils, and IgE), it follows that utilizing existing CT data while also having the concurrent retrospective benefit of known response to biologic therapy would allow this question to be most efficiently addressed without exposing any of the subjects to the harms of radiation solely for research purposes. Furthermore, our use of a learning cohort retrospectively constructed at the University of Michigan and a prospectively constructed validation cohort from the University of Calgary will allow us to generate more robust results than normally found in retrospective studies since we will be using a geographically distinct validation model.

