6.2 MORPHOMICS ANALYSIS AND PHENOTYPING

Compute height-normalized measures to control for height-related correlation, e.g., Skeletal Muscle Index = (Skeletal Muscle Area / Height²). Center and scale morphomics measures into standard deviation units, stratified by sex, to control for sex differences. (Optionally/additionally, convert morphomics measures into sex- and age-adjusted percentiles using the Reference Analytic Morphomics Population (RAMP), to simultaneously control for sex- and age-related correlation). The following analyses will be performed on both the UM and UC cohorts combined. Classification and regression tree (CART) will be utilized to develop individualized decision rule on SARP class based upon morphomic measures. In addition, Unsupervised learning techniques will be carried out to identify novel clusters for morphomic phenotypes in these cohorts.

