7.1.9 DATA HANDLING AND RECORD KEEPING

7.1.9.1 DATA COLLECTION AND MANAGEMENT RESPONSIBILITIES

Study oversight will be performed by the principal investigators and the co-investigator and the University of Michigan data analysis team. The study database will be developed on servers managed by MICHRI (the CTSA supported clinical research infrastructure) at the University of Michigan. Web-based data entry and management, as well as the creation and export of study reports for the safety committee will be provided by the University of Michigan under the guidance of the data management core. The study will use the REDCap clinical trial software platform for electronic data capture and clinical data management, as the basis for our custom-designed data entry and management system. Protocols for the transfer of data, with careful attention to data integrity, will be written by experienced programmers and stored in the database. Data collection is the responsibility of the research staff. The investigator is responsible for ensuring the accuracy, completeness, legibility, and timeliness of the data reported.

CT scans anonymization will be performed through existing processes in the analytic morphomic group. Scans will be selected using software that connects directly to the institution's existing PACS system. Once an appropriate scan is identified, it will be downloaded and processed through the morphomic lab's anonymization software. This system removes the patient information stored in each image file's DICOM header, which contains attributes such as name, patient ID, date of birth, etc. All patient identifying data is removed, and a unique identifier (UI) is created and stored in the Patient ID attribute. The UI takes place of the medical record number (MRN) throughout the life of the project. The key connecting this UI with the patient MRN will be maintained and controlled by the project PIs.

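### Height, sex and age are the only stated corrections to the CT measures; if muscle quality means CT density, the primary predictor may partly reflect contrast use and tube voltage

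*Combined protocol and SAP*

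**What the plan says.** The primary endpoint in the synopsis (Section 1.1) is: "Determine the cutoff value in chest wall muscle size/quality that optimally classifies patients" by whether exacerbations fell. Quality is not defined there or in Section 2.2, which says only that intercostal muscle size and quality can be measured. The same section gives examples of morphomic measures: "such as fat distribution, bone mineral density, and muscle density and size".

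The scans are existing images. Section 4.2 explains: "Many asthmatics undergo CT scans for various reasons". Section 4.1 selects Michigan scans by body region and by timing relative to the start of the biologic. Section 7.1.9.1 adds that an appropriate scan is identified through software linked to the image archive, without saying what makes a scan appropriate.

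Three corrections are stated:
- Height: "Height-normalized measures will be computed to control for height-related correlation" (Section 4.1; the example is a muscle area).
- Sex and age: Section 4.1 says "Morphomics analysis will be run with measures centered and scaled into standard deviation units, stratified by sex and age", while Section 6.2 says "Center and scale morphomics measures into standard deviation units, stratified by sex, to control for sex differences" and makes sex- and age-adjusted reference percentiles optional or additional.
- Reference population: it "will be used to generate additional variables that offer a population-based control for sex and age" (Section 4.1).

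The abstraction list in Section 4.1 holds clinical variables only. The models in Section 6.3 name no acquisition variable. Contrast, tube voltage, slice thickness and reconstruction kernel appear nowhere as a selection rule, recorded item, stratum, covariate or sensitivity analysis.

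**The concern.** CT density is an attenuation value, and attenuation depends on intravenous contrast and tube voltage. Scaling by height, sex and age cannot remove that dependence. Elastic net and tree ensembles cannot adjust for a variable they are not given.

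Three consequences follow if quality is read as density:

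1. Technique unrelated to outcome adds noise and weakens a true marker.
2. Technique related to outcome can create a spurious marker. Section 4.2 makes such a link plausible: it says stable patients are seldom scanned, so the reason for the scan may influence both the imaging protocol and the disease state.
3. If technique differs between Michigan and Calgary, a cutoff derived at one site can misclassify at the other for technical reasons. The geographically separate validation cohort is the plan's main claim to robustness, and nothing recorded would show that a failed validation was technical.

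**Working it through.** The plan gives no effect size, SD or error rate for this point, so there is no figure to reproduce. The calculation below is illustrative.

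**Inputs from the documents.** About 300 Michigan patients (Section 4.1) and about 15% non-responders (Section 4.1): 0.15 × 300 = 45 non-responders and 255 responders.

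**Assumptions, not in the documents.** Measured density = biology (SD 1) + d × contrast indicator. The shift d is 0.25, 0.5 or 1 SD. Contrast is used in half the scans overall. Where an imbalance is examined, contrast use is 60% in one response class and 40% in the other.

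**Noise.** With contrast share p = 0.5 and unrelated to outcome, the correlation of density with outcome is multiplied by 1/√(1 + p(1−p)d²) = 1/√(1 + 0.25d²).

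**Spurious difference.** With no true association, the mean difference between classes is 0.2d. The within-class variance is 1 + 0.6 × 0.4 × d² = 1 + 0.24d². So SE = √[(1 + 0.24d²)(1/45 + 1/255)], where √(1/45 + 1/255) = 0.162. With k = 0.2d/SE, a two-sided 5% test rejects with probability Φ(−1.96 + k) + Φ(−1.96 − k).

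| d | Correlation multiplied by | False difference (SD) | SE (SD) | k | Rejection rate |
|---|---|---|---|---|---|
| 0.25 | 0.992 | 0.05 | 0.163 | 0.31 | 6.1% |
| 0.5 | 0.970 | 0.10 | 0.166 | 0.60 | 9.2% |
| 1 | 0.894 | 0.20 | 0.180 | 1.11 | 19.9% |

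The technique variance belongs in the SE. Leaving it out at d = 1 gives 0.20/0.162 = 1.24 SE and a rejection rate of about 24%, which is too high.

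**Cutoff moved to the second site.** Suppose contrast raises density, low values are flagged, and the cutoff c flags 15% at Michigan with 50% contrast use: 0.5Φ(c − d) + 0.5Φ(c) = 0.15. Apply the same c at Calgary, on the same scale and with identical biology, at contrast share s: sΦ(c − d) + (1 − s)Φ(c).

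| d | Flagged at s = 20% | Flagged at s = 80% |
|---|---|---|
| 0.25 | 16.7% | 13.3% |
| 0.5 | 18.4% | 11.6% |
| 1 | 21.1% | 8.9% |

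At d = 1 the cutoff flags 25.2% of unenhanced and 4.8% of enhanced scans.

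**The case against.** The strongest reply is that much of this is inferred, and several parts of it stand.

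- A reader might infer that the predictor is shown to measure scan technique. The documents do not support that. Quality is never equated with attenuation; density is the natural reading of Section 2.2 but remains a reading. Muscle size is less directly affected.
- A reader might infer that scans are chosen by date alone. They are chosen by region and timing, and the undefined appropriateness step in Section 7.1.9.1 could include technique.
- A reader might infer mixed technique at both hospitals. Section 4.1 describes scan identification for Michigan only, and Section 4.2 calls the Calgary cohort prospectively constructed. How Calgary scans were acquired is not described.
- The shift, the contrast share and the imbalance are all assumed. At 0.25 SD the harm is small.
- The plan specifies no 5% test. It seeks a cutoff and uses penalised and tree models with performance measures, so the rejection rate is a yardstick and not a property of this plan.
- Evaluation at Calgary is a partial safeguard: an artefact confined to Michigan would tend to fail there, although one shared by both sites would survive. If scaling is done within each cohort, the mean shift between sites drops out. The plan does not say which is done.

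What does not stand is that the plan already covers the matter. Followed as written, the stated scaling rule leaves technique variation in any density measure. Section 7.1.9.1 says of the anonymization software: "This system removes the patient information stored in each image" header. It does not say that acquisition fields are kept or used.

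**Conclusion.** The concern holds in conditional form. The plan normalises for height, sex and (optionally in Section 6.2) age, and is silent on contrast and tube voltage. If quality means CT muscle density, the primary predictor may partly reflect technique.

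The size cannot be found from the documents. Under assumed contrast shifts of 0.25 to 1 SD in half the scans, the loss of correlation runs from negligible (0.99) to moderate (0.89). A 20-point imbalance between response classes raises an illustrative 5% error rate to between 6% and 20%. A cutoff meant to flag 15% could flag anywhere from 9% to 21% at a site with 80% or 20% contrast use, if both sites are on a common scale. The result depends on the true shift, the mix of techniques, and whether technique tracks outcome or site. Unless technique is recorded, none of these can be assessed afterwards. The point should be settled before the images are analysed.

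**What to change.** In Sections 4.1 and 6.2:

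1. Define muscle quality, and say whether it is an attenuation measure.
2. Extract contrast status, tube voltage, slice thickness and kernel from the image header before anonymization.
3. Adjust density-type measures for contrast status before modelling, as a two-level stratum, or with contrast and tube voltage as covariates if strata become too small.
4. State whether scaling is within or across cohorts, and reconcile the sex-and-age wording of Section 4.1 with the sex-only wording of Section 6.2.
5. When several scans are equally eligible, prefer the unenhanced one.
6. Tabulate technique by site and by response class.
7. As a sensitivity analysis, repeat the primary cutoff analysis in the largest single-technique subset. Do not repeat the full high-dimensional model there.

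The cost is header extraction in the imaging pipeline and some added wording. Scaling strata would be about half their size at 50% contrast use. The sensitivity analysis would be imprecise: at that share it would hold perhaps 22 Michigan non-responders (0.5 × 45 = 22.5), so it could show a gross technique effect but not exclude a modest one.
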